### 10.3.2 Time to Event

Progression-free survival, response interval and overall survival will be summarized using the Kaplan-Meier method.

Progression-free survival is defined as the time from the date of treatment initiation until the date that disease progression criteria are met or the date death without progression, or is censored at the date of last disease assessment without evidence of progression.

Response interval is defined among patients achieving a complete or partial response, from the date that response is achieved until the date that disease progression criteria are met or death without progression, or is censored at the date of last disease assessment without evidence of progression.

Overall survival is calculated from the date of treatment initiation to the date of death, or censored at date of last contact.

The association between somatic mutational load and time to event outcome in MCM and ALM can be assessed using log rank tests. Kaplan-Meier curves by mutation status will be presented.

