### 1.8.2 Mutational Burden in Metastatic Melanoma

Malignant melanoma contains the highest prevalence of somatic mutation per megabase, especially high base-pair mutation rate attributable to UV exposure, in comparison to other cancers. The highly variable prevalence of somatic mutations among each cancer genome, between 0.001 per megabase (Mb) to more than 400 per Mb, is likely contributed by known mutagenic exposure, mismatch repair machinery defects, or the duration of cellular damage/replication error of passenger mutations between the fertilized egg to the time of samples analysis in cancers arise from self-renewing tissues (37, 38).

High mutational burden correlated with overall survival in patients with cutaneous melanoma treated with ipilimumab (39) or lung cancer treated with anti-PD1 (40).

[figure not shown]

Figure 1 Mutational Landscape of Tumors According to Clinical Benefit from Ipilimumab Treatment. Panel A shows the mutational load (number of nonsynonymous mutations per exome) in the discovery and validation sets, according to status with respect to a clinical benefit from therapy. Panel B depicts the Kaplan-Meier curves for overall survival in the discovery set for patients with more than 100 nonsynonymous coding mutations per exome and patients with 100 or fewer mutations(39).

Although the predictive markers research and discovery in cutaneous melanoma has made great progress, there is a paucity of data on the biomarkers predictive of response in patients with MCM and ALM receiving checkpoint inhibitor therapy and very little data in any patient population receiving combination CTLA4 and anti-PD1 inhibitor therapy. Furney et.al observed an average of twelve to sixty-six non-synonymous single nucleotide variants (SNV) in whole exome sequencing of both MCM and ALM (41, 42), at least 5-10 fold less mutational load than typically seen in cutaneous melanomas. Paucity of data from next-generation whole genome/exome sequencing in MCM and ALM, with less than 10 study subjects from each disease, limits analytical power and is subjected to ascertainment bias.

A preliminary study on whole exome sequencing of anorectal, nasopharyngeal and vulvovaginal MCM demonstrated unique mutational pattern between MCM and cutaneous melanoma. Additionally, analysis of each MCM subgroup could also distinguish each subset of MCM by different mutational profiles (Gorden et al; SMR 2015)

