2.3 To determine progression-free survival (PFS), and overall survival (OS) in each cohort

2.4 To determine whether pre-existing immune cells infiltrate, as well as Ki-67 and PD-L1 expressing cells at the invasive tumor margin correlate with clinical response to a combination of CTLA-4 and PD-1 blocking therapy

2.5 To evaluate subject's cancer genomic landscape using whole exome sequence profiling, identify the mutational pattern, and the frequency of somatic mutations and their relationship to tumor response in MCM and ALM, as well as subject's cancer genomic landscape using whole exome sequence profiling and utilize bioinformatic tools to translate mutations in exomes to identify specific driver mutations in MCM and ALM

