#### 9.2.2 Tumor Whole Exome Sequencing

At the end of the study, unstained slides will be batched and shipped to [name] at University of Colorado where exome sequencing will be performed.

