#### 9.2.3 Assessment of Tumor's Mutational Burden and Driver Mutations

Analysis will utilize matched paired of (i) tumor, and (ii) normal adjacent stromal tissue from pre-treatment samples. Tissue dissection will be done by means of macrodissection. Paired normal tissue will serve as control and reference sequence for each patient's tumor and differentiation of germline mutations/polymorphisms from true somatic mutations. Tumor and normal stromal tissue will undergo DNA extraction according to standard FFPE DNA extraction protocol. DNA fragmentation, DNA library preparation, exome enrichment, automated cluster generation, paired-end sequencing, and base calling will be performed at University of Colorado at the end of the study.

Human exome sequencing from gDNA will include initial DNA sample QC using NanoDrop and Qubit. Exome sequences will be captured using the Agilent SureSelect Exome enrichment kit, along with associated QC, and libraries constructed using standard Illumina library preparation. Samples will be sequenced on an Illumina HiSeq2000 using PE100-125bp read length chemistry, designated 400x average coverage for the cancer and 200x for normal exomes with approximately 9-11 Gb output. Standard exome bioinformatic analysis will include mapping and alignment (BAM file), QC, coverage, sequence variation (SNPs/Indel report (.VCF file)), VCF annotations, functional prediction, and population frequency. Deliverable will include raw data FASTq and analysis files (.VCF)

Data cleanup, variant discovery, annotation, and evaluation will be performed at University of Colorado. Mutational load will be quantified as the number of non-synonymous somatic mutations per megabase (MB). Raw and annotated exome sequencing data will be available at MRFBC Cloud library for future data mining and comparison.

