## 10.2 Sample Size Considerations

The primary endpoint is objective response rate (CR+PR) as defined earlier in the metastatic MCM population. ORR in the ALM populations will be exploratory. The response rate with current standard therapy is approximately 23-25%(65). Secondary clinical endpoints include, median PFS and OS, 6 month landmark PFS and 1 year landmark OS. Biomarker exploratory endpoints will include: 1) the relationship of CD8 T cell score at the invasive margin and tumor response for each malignancy and 2) the relationship with tumor mutational frequency using whole exome sequencing and response. Bioinformatic tools will be used in an attempt to identify recurring driver mutations in MCM (as well as ALM).

The sample size is based on the primary endpoint objective response rate (ORR). The null hypothesis that the ORR is at most 25% will be tested against a one-sided alternative. If the ORR is less than 25%, we will consider this therapy not worth pursuing. If it is more than 25%, the therapy is considered worth pursuing. With 39 patients, the study would have 90% power at a significance level of 10% if the true ORR is 45%. To take into consideration a potential non-evaluable or dropout rate of 20%, 49 patients with MCM (cohort A) will need to be enrolled into this study. The exact binomial calculation is used.

Given the less frequent occurrence of metastatic melanoma involving ALM subtypes, we will plan to enroll only 24 patients with ALM (cohort B). This should allow the accrual to both cohorts to finish at roughly the same time. Analysis of activity Cohorts B and the biomarker data will be primarily descriptive and exploratory.

Patients who enroll in this trial but do not receive the immune checkpoint inhibitor combination, or those for whom tissue is not submitted (see section 9.0) and therefore cannot be classified into a predictive factor group, will be deemed unevaluable for the primary endpoint of the study; available information on these patients will be described in the final report.

The overall accrual rate is anticipated to be 2-4 patients per month on each cohort, based on past experience among each institution in the Melanoma Research Foundation Breakthrough Consortium , resulting in expected accrual duration of about 20-24 months. The trial's primary analyses are planned to occur at 6 months after each patient has received the treatment.

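### Section 10.3.2 plans log-rank tests for a continuous mutational load without a grouping rule; an exploratory Cox model on continuous load is a cheap improvement

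*Combined protocol and SAP*

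**What the plan says.** Section 10.3.2 has two sentences on this point: "The association between somatic mutational load and time to event outcome in MCM and ALM can be assessed using log rank tests" and "Kaplan-Meier curves by mutation status will be presented". Section 9.2.3 makes mutational load a quantity, the count of non-synonymous somatic mutations per megabase.

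The only load cut in the document is in a figure legend in Section 1.8.2. It describes a cited ipilimumab study that compared patients with "more than 100 nonsynonymous coding mutations per exome and patients with 100 or fewer mutations". The plan does not adopt it. The same section reports "an average of twelve to sixty-six non-synonymous single nucleotide variants (SNV) in whole exome sequencing of both MCM and ALM".

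Section 10.3.1 compares continuous factors between responders and non-responders with a Wilcoxon rank sum test, which needs no cut. Section 9.2.2 places exome sequencing late: "At the end of the study, unstained slides will be batched and shipped to" the sequencing laboratory.

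On status, Section 10.2 says "Analysis of activity Cohorts B and the biomarker data will be primarily descriptive and exploratory". Objective 2.5 relates mutations to tumour response. Objective 2.3 is "To determine progression-free survival (PFS), and overall survival (OS) in each cohort". No listed objective relates load to PFS or OS.

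**The concern.** Three things are left open:

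- How a continuous load becomes groups for a log-rank test.
- Whether *mutation status* means high or low load, or presence of a driver mutation.
- Whether MCM and ALM are tested separately, pooled or stratified.

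Two statisticians could run different analyses and both claim to follow the plan.

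There is also an efficiency question. Even if a split is fixed in advance, it discards the ordering within each group. In a sample this small that costs power unless the true effect is a step near the cut. At stake is how much the trial can learn about load and survival in two rare melanoma types, not its main conclusion.

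**Working it through.** **1. The plan's own figure.** Section 10.3.2 gives no number for this analysis. The only design calculation is in Section 10.2. With n = 39, null 25%, alternative 45% and success at 14 or more responses, the exact binomial gives type I error 0.086 and power 0.905, so the stated 10% and 90% reproduce. 39 / (1 − 0.20) = 48.75, rounded up to 49, also as stated.

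**2. Inputs.** From Section 10.2: 39 evaluable MCM; 24 ALM enrolled; 20% non-evaluable. Applying the 20% to ALM as well (an assumption) gives 24 × 0.80 = 19. The documents give no effect size, censoring or load distribution for this analysis. Those below are assumptions: exponential event times, normal log-load, log-linear effect, two-sided 5%.

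**3. Information kept by a median split.** For a normal covariate with a log-linear effect, the split log-rank test has relative efficiency 2/π = 0.64. Worked for 30 events and a hazard ratio (HR) of 1.5 per SD (β = ln 1.5 = 0.405):

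- Continuous: Φ(√30 × 0.405 − 1.96) = Φ(0.26) = 60%.
- Split: log HR = 2√(2/π) × 0.405 = 0.647, so Φ(√30 × 0.647/2 − 1.96) = Φ(−0.19) = 43%.

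These large-sample formulas run a few points high at this size, so the table uses simulation.

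**4. Simulated power (%), continuous Cox score test vs within-cohort median-split log-rank** (20,000 replicates per cell; stratified by cohort when both are included):

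| Patients | Censored (events) | HR 1.3 per SD | HR 1.5 | HR 1.75 | HR 2.0 |
|---|---|---|---|---|---|
| 39 MCM | 20% (31) | 28 vs 20 | 54 vs 38 | 80 vs 59 | 92 vs 75 |
| 39 MCM | 40% (23) | 22 vs 16 | 44 vs 30 | 69 vs 49 | 84 vs 63 |
| 39 MCM + 19 ALM | 20% (46) | 38 vs 26 | 70 vs 50 | 92 vs 75 | 98 vs 88 |
| 39 MCM + 19 ALM | 40% (35) | 30 vs 21 | 59 vs 41 | 84 vs 64 | 95 vs 80 |

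With no effect, both tests reject in 5.1 to 5.8%. Early OS could be more heavily censored. At an assumed 70% censoring (about 12 events in 39 MCM), HR 1.5 per SD gives 26% vs 18%.

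**5. Where the ranking changes.** For a true step of HR 2.0 at the median, the continuous model has 31% and the split 37% (n = 39). For the same step at the 75th percentile, the figures are 20% and 15%.

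**6. Cohort handling.** With HR 1.5 per SD in MCM and no effect in ALM, the stratified continuous model has 39% power, the stratified median split 27%, and the continuous model in MCM alone 54%. If the cohorts differ by 1 SD in load and twofold in hazard with no effect within either (49 + 24 patients), unstratified pooling rejects in 15% (split) to 17% (continuous). Stratified tests reject in about 5 to 6%. At HR 1.5 per SD and 20% censoring, the 95% CI is about the HR multiplied or divided by 1.5 in 39 MCM and by 1.9 in 19 ALM. Cohort estimates are therefore descriptive.

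**7. Scale of the covariate.** Zero counts may need an offset before taking logs. The 12 to 66 variants in Section 1.8.2, over an assumed 30 to 50 Mb exome, give 12/50 = 0.24 to 66/30 = 2.2 per Mb. With an offset of 1, doubling the load moves log2(load + 1) by log2(1.48/1.24) = 0.26 to log2(5.4/3.2) = 0.75, not by 1. A coefficient on that scale is not a hazard ratio per doubling of load.

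**The case against.** The strongest reply is that little depends on this test. The wording is permissive, the biomarker work is declared exploratory, and no decision, error rate or sample size rests on it. That stands, and it makes the point minor.

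A second reply is that a log-rank test is valid once a cut is fixed in advance, so only the missing definition is a documented gap; preferring Cox rests on assumed effects. This stands in part. Late sequencing means a cut could still be fixed before any load data exist. That would close the specification gap but leave the loss in step 4 unless the effect is a step near the cut. If *mutation status* means presence of a driver mutation, the log-rank test suits that grouping.

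Third, neither method is strong for modest effects: at n = 39 and HR 1.3 to 1.5 per SD, the continuous model reaches only 22 to 54%. That is correct.

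A reader might infer that the cut will be chosen by looking at outcomes. Taking the best of 13 cuts would raise a nominal 5% error to about 26 to 28%, but nothing in the plan proposes such a search. A reader might also infer that the 100-mutation cut will be used and leave almost no one in the high group. That cut belongs to a cited study, is in a different unit and is not adopted, so it does not measure a loss under the plan as written.

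**Conclusion.** The point holds as a minor, exploratory one. The grouping rule and the meaning of *mutation status* are absent, and cohort handling for this test is not stated, although the objectives lean towards cohort-specific reporting. A continuous model generally uses the sample better: at HR 1.5 per SD and 20 to 40% censoring, the gain over a median split is about 14 to 20 percentage points. This rests on a log-linear effect, normal log-load and exponential times, none of which the documents supply.

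The documents do not support saying that the log-rank test is invalid, that Cox is better under every truth (step 5 shows otherwise), or that the trial's main result is affected. The Wilcoxon test in Section 10.3.1 is a precedent for avoiding a cut; being rank-based, it is not one for a log-linear model.

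**What to change.** In Section 10.3.2, for load only, replace the log-rank sentence with the following:

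- Fit Cox models for PFS and for OS with log-transformed load as a continuous covariate. Fix the transform and any zero-count offset before sequencing.
- Report the hazard ratio per SD (saying which SD), or between stated load values such as the quartiles, with 95% CI. Do not label it per doubling if an offset is used.
- Give MCM and ALM estimates separately, alongside the cohort-stratified estimate, and label all of them exploratory.
- Add log-linearity and proportional-hazards checks as labelled sensitivity analyses. Section 1.6 describes a survival plateau with ipilimumab, so proportional hazards should not be taken for granted.
- Keep Kaplan-Meier curves by a within-cohort median split fixed in advance, for display only.
- Define *mutation status*. If it means presence of a driver mutation, name the genes and keep the log-rank test for that grouping.

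The cost is SAP wording and minor programming before the end-of-study sequencing, with no extra patients, samples or data. The downside is that the model assumes a log-linear effect and does slightly worse than a split if the truth is a step at the median. The stratified estimate also assumes an effect common to both cohorts, which is why the separate estimates should stand beside it.

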### 10.3.3 Toxicity

The toxicity of nivolumab in combination with ipilimumab is well established in the melanoma patient population (9-11). As this treatment represents standard of care for this patient population, a formal analysis of toxicity is not considered as an endpoint for this study. As such, only the incidence of severe adverse events (immune related AEs) will be collected at the end of each patient's treatment course. A single page form will be provided to collect this summary

information. (see Section 7).

## **11.0 RECORDS TO BE KEPT**

The original signed consent form will be kept with the patient's other study documentation (e.g., the hospital or clinic chart, the case report form).

A data manager will be assigned to this protocol to ensure that data is collected and reviewed on a continuous basis.

The following forms will be submitted to the electronic data capture (eDC) system:

Forms:

- 1) Patient Registration Form
- 2) **On-Study Form** (within 2 weeks after initiation of treatment)
- 3) **Measurement Form** (at baseline and then every 12 weeks) until treatment completion. For patients with persistent SD or response at time of treatment discontinuation, subsequent imaging will be every 3 months until 2 years from treatment initiation, then every 6 months during year 3, and then yearly thereafter for years 4 and 5 per standard of care)
- 4) **Treatment Form (within 4 weeks of decision to stop treatment for each subject)**  

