## 5.2 Duration of Therapy and Response Assessment

All patients will receive nivolumab administered IV combined with ipilimumab administered IV every 3 weeks for 4 treatment cycles per standard of care (Induction) then continue with nivolumab administered IV per standard of care until progression, intolerable toxicity, or a maximum of 48 doses, whichever comes first (Maintenance). Patients exhibiting complete response (CR) should continue nivolumab monotherapy at least 12 weeks beyond documentation of CR, if possible. Patients will be treated within participating sites within the MRFBC. Commercial drugs will be used in this protocol and will not be supplied by the study.

Patients will be evaluated for response at approximately 12 weeks following the initiation of treatment and then approximately every 12 weeks. Response will be evaluated by the study investigators using the Response Evaluation Criteria in Solid Tumors (RECIST) criteria ,v1.1. (See appendix C). Following completion of therapy, patients with evidence of SD, PR or CR will have CT scans every 3 months for 2 years, then every 6 months during year 3 and then yearly thereafter for years 4 and 5. Attention will be paid to the time of disease progression. Both responding and non-responding patients will be followed until death.

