**Appendix F**  
**Suggested Schedule of Events**

Assessment 6 wks = 1 cycle	Baseline	Induc- tion			Maintenance	End of Treatment	Disease Progression	Follow-up/ Safety Follow-up
	Within 4 weeks	Cycle 1	Cycle 1	Cycle 2	Cycle 3 and after			
		Day 1	Day 22	Day 1	Day 1			
Informed consent	x							
Assignment identification numbers	x							
Medical history and demographics e	x							
Complete physical exam	x							
Weight	x							
Height	x							
ECOG performance status	x					x	x	x
Hematology&Chemistry lab c,d	x		x	x	x	x	x	
Adverse events			x	x	x	x	x	x
Imaging Studies a	x a				x a			x a
Submission of Archival tumor for review	x							
Fresh tumor biopsy				x b				
Peripheral blood correlates	x	x		x	x			
Microbiota correlates		x	x				x	

a. Non-CNS Imaging should include a chest, abdomen and pelvis CT. Imaging of other sites should be obtained when clinically indicated. If follow up scans

Protocol Number: CA209763

Version dated: January 31, 2019

indicate partial or complete response, a repeat confirmatory scan should be obtained within 12 weeks (but no sooner than 6 weeks). Baseline imaging should be done within 4 weeks prior to registration, then every 12 weeks if patient is < 2 years from study entry, then every 6 months (+/- 4 weeks) until 5 years from study entry

- b. Fresh tumor biopsy is expected in 25% of patients (N=25; 10 MCM and 5 ALM patients) to consent to on-treatment biopsies. Please refer to appendix G for detail. This can be collected within weeks 6-8.
- c. Hematology Labs should include CBC with differential (hemoglobin, hematocrit, white blood cells, platelets, neutrophils, lymphocytes, eosinophils and monocytes)
- d. Chemistry Labs should include albumin, amylase, lipase, BUN, creatinine, ALT, AST, LDH, serum alkaline phosphatase, direct and total bilirubin, glucose, total protein, sodium, potassium, chloride, HCO3, calcium, uric acid and CPK. Labs should also include TSH and free T4 if TSH is elevated. Sites should follow their institutional guidelines for hematology and Chemistry labs.
- e. Updated history and limited physical examination are recommended to be performed every 3 weeks for the first two cycles, then on the first day of subsequent cycles.

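### The protocol conflicts with itself on whether a patient who stops treatment in induction, before the week-12 scan, is still assessed for response

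*Combined protocol and SAP*

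**What the plan says.** Two places tie assessment after treatment to a known disease status.

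- Section 11.0 requires the Measurement Form "at baseline and then every 12 weeks) until treatment completion". It continues: "For patients with persistent SD or response at time of treatment discontinuation, subsequent imaging will be every 3 months", with longer intervals in later years.
- Section 5.2 says: "Following completion of therapy, patients with evidence of SD, PR or CR will have CT scans every 3 months for 2 years".

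Two places set a calendar with no condition on treatment or response.

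- Section 5.2, same paragraph: "Patients will be evaluated for response at approximately 12 weeks following the initiation of treatment and then approximately every 12 weeks".
- Appendix F, footnote a: after baseline, imaging is "then every 12 weeks if patient is < 2 years from study entry". The appendix is titled "Suggested Schedule of Events". Its imaging row, as it reads in the available text, has marks at baseline, in maintenance and in follow-up, and none under End of Treatment.

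Other provisions bear on the same patient. Sections 10.1 and 10.2 make a patient unevaluable for the primary endpoint only if the combination was not given or tissue was not submitted. Appendix D, item 4.3, runs best overall response from the start of treatment to progression or recurrence. Section 8.0 removes patients only for withdrawal of consent and keeps documenting dates of progression and death. Section 5.2 adds: "Both responding and non-responding patients will be followed until death". Section 11.0 lists a Follow-up Form every 3 months. In Section 10.3.2, a patient without a PFS event "is censored at the date of last disease assessment without evidence of progression".

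**The concern.** Stopping during induction is foreseeable. The background section cites Grade 3 or 4 events in 54% and 55% of patients on the combination in two randomized trials, and Section 7.0 itself discusses ending treatment after severe toxicity. A site that works from the list of forms in Section 11.0 could conclude that nothing more is to be measured in such a patient. A site that works from Appendix F would scan at week 12.

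The patient counts in the primary ORR either way. If no scan is done, a response that appears after stopping goes unrecorded, and whether it is missed depends on how well treatment was tolerated. For PFS, progression is still to be recorded, but without scheduled scans it may be found late, which would affect the median and the 6-month landmark named in Section 10.2.

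**Working it through.** **1. Timeline.** Induction is four doses at 3-week intervals, so doses fall at about weeks 0, 3, 6 and 9. The first response evaluation is at about week 12. A patient who stops after one, two or three doses had the last dose at week 0, 3 or 6 and has no post-baseline assessment when treatment ends.

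**2. Each rule applied to that patient.**

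- Section 11.0, Measurement Form: the 12-weekly requirement ended with treatment. The continuation needs SD or response at discontinuation, which has not been assessed. Not covered.
- Section 5.2, post-therapy sentence: needs evidence of SD, PR or CR. Not covered.
- Section 5.2, week-12 sentence: the clock starts at treatment initiation, with no on-treatment condition. Covered.
- Appendix F, footnote a: the clock starts at study entry, with no condition on treatment or response. Covered, but only as a suggestion.
- Section 8.0 and the Follow-up Form: progression and death dates are kept. Neither mentions tumor measurements or response, and the form's content is not described.

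Two rules include the patient and two leave the patient out. The only form named for measurements is one of the two that leave the patient out.

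**3. Collection against endpoint.** Best overall response runs to progression, and evaluability needs one combination dose plus tissue. The Measurement Form rule is therefore narrower than the endpoint it serves. No section says how an evaluable patient without a post-baseline scan is counted.

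**4. The plan's own figure.** Section 10.2 gives a null ORR of 25%, an alternative of 45%, one-sided 10%, n = 39 and the exact binomial. The document states no cut-off, so I derived one.

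- P(X ≥ 13 | 39, 0.25) = 0.1545 and P(X ≥ 14 | 39, 0.25) = 0.0862, so the rule is at least 14 of 39.
- Power: P(X ≥ 14 | 39, 0.45) = 0.9048.
- Enrolment: 39 / 0.80 = 48.75, rounded up to 49.

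The stated design reproduces.

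**5. Illustration of size.** Let m be the share of the 39 who stop before any scan. The values of m are assumptions. Suppose none of these patients is scanned, all count as non-responders, and their true response rate is also 45%. The observable rate is 0.45 × (1 − m).

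- m = 5%: 0.4275, power 84.8%
- m = 10%: 0.405, power 77.1%
- m = 20%: 0.36, power 56.5%

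Fixing the number of unscanned patients at 2, 4 or 8 and computing P(X ≥ 14 | 39 − k, 0.45) gives 85.1%, 77.7% and 56.2%, so the result does not depend on the shortcut.

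If half of these patients are scanned after all, the rate is 0.45 × (1 − m/2) and power is 87.9%, 84.8% or 77.1%.

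Under the null, the same counting rule lowers the type I error: P(X ≥ 14 | 39, 0.25 × (1 − m)) is 6.0%, 4.0% or 1.5%. It costs power and does not create false positives.

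**6. Why the counting rule should be written down.** Suppose such patients were instead dropped, all were true non-responders, and the overall ORR was 25%. At m = 10%, 35 remain, the apparent rate is 0.25 / 0.90 = 0.2778, the cut-off for n = 35 is 13, and the type I error is 14.75% against a nominal 10%. This is a worst case.

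**The case against.** A reader might infer that no response data at all are required for early stoppers. The documents do not support that. The week-12 sentence of Section 5.2 applies to patients generally from treatment initiation, and Appendix F schedules 12-weekly imaging whatever the treatment status and marks imaging in follow-up. That Appendix F is only suggested weakens it but does not remove it.

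A reader might also infer that these patients are censored for PFS at about day 0. That would require no week-12 evaluation and no follow-up information. Section 8.0 calls for progression and death dates in everyone who has not withdrawn consent, Section 5.2 follows all patients until death, and a Follow-up Form is due every 3 months. What remains is that dates found without scheduled scans may be late.

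A third inference is that such patients would be dropped from the primary analysis under the 20% allowance in Section 10.2. That allowance is for planning enrolment. The evaluability rule keeps a dosed patient with tissue in.

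Finally, the power figures combine an assumed early-stopping rate with complete loss of scans. The 56.5% figure needs 20% early stopping and no scan in any of those patients. These objections limit the point. They do not settle which instruction a site should follow or which form records the result.

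**Conclusion.** The point holds as an internal inconsistency about data that feed the primary endpoint, and it should be corrected. It is not an error in the sample size, which reproduces at 39 evaluable and 49 enrolled. Nor is it a demonstrated loss of data, since two provisions do call for the scan.

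The size cannot be fixed from the documents because they give no rate of stopping before week 12. Over an assumed range of 5% to 20%, the power loss under a literal reading of Section 11.0 is between about 6 and 34 percentage points (90.5 − 84.8 = 5.7; 90.5 − 56.5 = 34.0). With half of these patients scanned it is between about 3 and 13 points (90.5 − 87.9 = 2.6; 90.5 − 77.1 = 13.4). These figures assume that early stoppers respond at the design rate of 45% and that the cut-off is 14 of 39. The effect on PFS is possible late dating of progression, which I have not quantified.

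**What to change.** Reconcile Section 5.2, Section 11.0 and the imaging row of Appendix F around one rule, for example: response assessment and the Measurement Form follow the 12-week calendar from first dose in every dosed patient, whether or not treatment has stopped and for whatever reason, until RECIST progression, death or withdrawal of consent, with the protocol's longer intervals in later years. State that the week-12 assessment is due in every dosed patient.

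The three places also differ on the later calendar. The 2-year mark runs from completion of therapy, treatment initiation or study entry, and years 4 and 5 are yearly in two places and 6-monthly in the third. These should be aligned in the same edit.

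In Section 10.1 or 10.3.1, add that evaluable patients with no post-baseline scan stay in the ORR denominator as non-responders. That follows from the existing evaluability rule and errs on the conservative side, while the assessment rule keeps such patients few.

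The cost is wording in the response-assessment, records and statistical sections and one table row, plus a few additional Measurement Forms and scans for early stoppers. Appendix F already suggests those scans.
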